9.7.3.15 Oocyte Utilization Rate and Oocyte Efficiency Index

The oocyte utilization rate (number of blastocysts transferred or cryopreserved divided by the number of oocytes retrieved) will be analyzed in a similar manner as ongoing implantation rate and will be applied to both the mITT and PP analysis sets.

³BB and above defined as: 6AA, 6AB, 6AC, 6BA, 6BB, 6BC, 6CA, 6CB, 6CC, 5AA, 5AB, 5AC, 5BA, 5BB, 5BC, 5CA, 5CB, 5CC, 4AA, 4AB, 4AC, 4BA, 4BB, 4BC, 4CA, 4CB, 4CC, 3AA, 3AB, 3AC, 3BA, or 3BB.

Date: 25 Apr 2018 E-Study Protocol-22377; Ver. 1.0 Supersedes: None Page 134 of 159

The oocyte efficiency index (cumulative number of ongoing pregnancies per oocyte retrieved) will be analyzed in a similar manner as ongoing implantation rate and will be applied to both the mITT and PP analysis sets.

9.7.3.16 Blastocyst Survival and Re-expansion after Cryopreservation

The number and percentage of blastocysts surviving cryopreservation will be tabulated. Further, among the blastocysts that survived cryopreservation, the number and percentage of blastocysts with reexpansion will be tabulated.

9.7.3.17 Number of Cryopreserved Cycles

The number of cryopreserved cycles initiated (i.e. cycles with subjects starting estradiol treatment), as well as the number and percentage of cryopreserved cycles with blastocyst transfer will be tabulated. Further, the total number of blastocysts transferred in fresh and cryopreserved cycles will be tabulated.

9.7.3.18 Circulating Levels of Endocrine Parameters

Blood samples drawn on stimulation day 1, stimulation day 5, end-of-stimulation, and oocyte retrieval will be analyzed for AMH, FSH, LH, estradiol, progesterone, inhibin A and inhibin B. Values below the lower limit of quantification (LLOQ) will be included as LLOQ/2. Values above the upper limit of quantification (ULOQ) will be included as ULOQ.

Each endocrine parameter and the change from baseline for post-baseline measurements will be tabulated for stimulation day 1 (baseline), stimulation day 5, end-of-stimulation and oocyte retrieval. For each parameter the change from baseline will be compared between treatment groups using a lognormal model. In this model change from baseline in log-transformed measurements will be the dependent variable and the linear predictor will include treatment as factor and baseline measurement (log-transformed) as covariate. The estimated treatment difference with 95% confidence interval will be presented on the original scale of measurement (i.e. exp-transformation applied to the log-transformed measurement) and accompanied by the p-value for test of no treatment difference.

Further, a population pharmacokinetic model will be used for evaluating the effects of subject characteristics on FSH concentrations and for assessing the variability in exposure. The modelling analysis will be described in a modelling analysis plan and the results reported separately from the clinical trial report.

Date: 25 Apr 2018 E-Study Protocol-22377; Ver. 1.0 Supersedes: None Page 135 of 159

9.7.3.19 Total Gonadotropin Dose, Number of Stimulation Days, and Number of Dose Adjustments

The total gonadotropin dose will be tabulated by treatment group. For the placebo group, both the actual total dose administered and the intended total dose (i.e. the sum of the dialed doses recorded by the subject) will be presented. In addition, the average daily dose, i.e. the total dose divided by the number of stimulation days, will be tabulated by treatment group.

The number of stimulation days will be tabulated by treatment group.

Investigator-requested decreases and increases of the gonadotropin dose will be captured during the stimulation period. The requested dose change (decrease / increase / no change) on stimulation day 5 will be tabulated. Furthermore, the total number of dose increase requests and dose decrease requests per subject will be tabulated.

These tables will be produced for all subjects who started stimulation, and for subjects who underwent triggering of final follicular maturation as well as separately according to whether triggering was done with hCG or GnRH agonist.

9.8 Safety Endpoints Assessments

9.8.1 General Considerations

Analyses for the safety analysis set will be conducted according to the actual treatment received.

Data will be presented by summary tables and listings. Categorical data will be summarized by treatment using the number and percentage of subjects in each category. For calculation of percentages, the denominator will be the total number of subjects in the respective treatment group in the safety analysis set. Continuous data will be summarized by treatment using number, mean, standard deviation, median, minimum, and maximum.

All individual subject data will be listed per subject and treatment as observed including any derived values.

Missing Data

Missing values will be treated as missing, except for causality, intensity, seriousness, and outcome of adverse events. A worst-case approach will be used: if causality is missing, the adverse event will be regarded as related to the IMP; if the intensity of an adverse event is missing, the adverse event will be regarded as severe; if seriousness is missing, the adverse event will be regarded as serious; if outcome

Date: 25 Apr 2018 E-Study Protocol-22377; Ver. 1.0 Supersedes: None Page 136 of 159

is missing, and no date of outcome is present, the outcome is regarded as 'ongoing'.

9.8.2 Secondary Safety Endpoints

9.8.2.1 Adverse Events

Adverse events will be coded using MedDRA. The version of MedDRA will be documented. Adverse events will be grouped according to start of IMP as follows:

- Pre-treatment adverse event, i.e. any adverse event occurring after signed informed consent and before start of IMP, or a pre-existing medical condition that worsens in intensity after signed informed consent but before start of IMP.
- Treatment-emergent adverse event in the fresh cycle, i.e. any adverse event occurring after start of IMP and before the end-of-cycle visit, or a pre-treatment adverse event or pre-existing medical condition that worsens in intensity after start of IMP and before the end-of-cycle visit.
- Adverse events in cryopreserved cycles, i.e. any adverse event occurring after initiation of a cryopreserved cycle and before the end-of-cycle visit, or a pre-existing medical condition that worsens in intensity after initiation of a cryopreserved cycle and before the end-of-cycle visit.

Treatment-emergent adverse events and adverse events in cryopreserved cycles will be presented in summary tables and listings. Pre-treatment adverse events will be presented in a listing only.

A treatment-emergent adverse event overview table will be prepared including the number of subjects reporting an adverse event, the percentage of subjects with an adverse event, and the number of events reported, for the following categories: all adverse events, severe adverse events, adverse reactions, adverse events leading to discontinuation, SAEs and deaths. An adverse reaction is an adverse event judged by the investigator to be related to IMP with a reasonable possibility.

Treatment-emergent adverse events will be tabulated by system organ class alphabetically and PT in decreasing order of frequency. The following will be presented: number of subjects reporting an adverse event, the percentage of subjects with an adverse event, and the number of events reported.

Summary tables will be produced for the following: all treatment-emergent adverse events, treatment-emergent adverse events by causality (reasonable possibility / no reasonable possibility), treatment-emergent adverse events leading to death, adverse events by intensity (mild / moderate / severe), treatment-emergent adverse reactions by intensity (mild / moderate / severe), serious treatment-emergent adverse events, treatment-emergent adverse events leading to discontinuation, treatment-emergent adverse events with an incidence of $\geq 5\%$ in any treatment group, and non-serious treatment-emergent adverse events with an incidence of $\geq 5\%$ in any treatment group.

Date: 25 Apr 2018 E-Study Protocol-22377; Ver. 1.0 Supersedes: None Page 137 of 159

Similar displays will be prepared for the adverse events in cryopreserved cycles.

9.8.2.2 Clinical Chemistry and Hematology Parameters

The circulating levels of clinical chemistry and hematology parameters including change from baseline will be tabulated for each time-point for each laboratory variable.

Shift tables will be prepared to compare baseline values to the end-of-stimulation and end-of-cycle values, using a categorization of low, normal and high values at each visit. Low, normal and high will be defined according to the reference ranges provided by the central laboratory.

A summary table will be prepared displaying the proportion of subjects who have at least one markedly abnormal value. The table will also include a break-down by classification of the baseline value. Markedly abnormal criteria for the safety laboratory variables will be specified in the SAP.

All laboratory values will be listed by subject number and time point. Values outside the reference range and markedly abnormal values will be flagged.

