- Number and percentage of blastocysts surviving cryopreservation and number and percentage of blastocysts with re-expansion after cryopreservation
- Number of cryopreserved cycles initiated within 12 months from the start of controlled ovarian stimulation, and number and percentage of cryopreserved cycles with blastocyst transfer

Date: 25 Apr 2018 E-Study Protocol-22377; Ver. 1.0 Supersedes: None Page 35 of 159

- Circulating concentrations of AMH, FSH, LH, estradiol, progesterone, inhibin A and inhibin B on stimulation day 5, end-of-stimulation and oocyte retrieval, and FSH population pharmacokinetic parameters
- Total gonadotropin dose, number of stimulation days and number of dose adjustments
- Frequency and intensity of adverse events
- Changes in circulating levels of clinical chemistry and hematology parameters and proportion of subjects with markedly abnormal changes
- Frequency and intensity of injection site reactions (redness, pain, itching, swelling and bruising) assessed by the subject during the stimulation period
- Proportion of subjects with treatment-induced anti-FSH antibodies, overall as well as with neutralizing capacity
- Frequency and intensity of immune-related adverse events
- Proportion of subjects with cycle cancellations due to an adverse event, including immunerelated adverse events, or due to technical malfunctions of the administration pen
- Proportion of subjects with OHSS, overall and by grade, and proportion of subjects with moderate/severe OHSS
- Proportion of subjects hospitalized due to OHSS and proportion of subjects undergoing paracentesis due to OHSS
- Rate of multi-fetal gestation, biochemical pregnancy, spontaneous abortion, ectopic pregnancy (with and without medical/surgical intervention) and vanishing twins in the fresh cycle and in the cryopreserved cycles
- Technical malfunctions of the administration pen

Post-trial Endpoints

- Cumulative live birth rate after the fresh cycle and cryopreserved cycles initiated within 12 months from the start of controlled ovarian stimulation
- Live birth rate in the fresh cycle and in the cryopreserved cycles
- Live birth rate of singletons born at term (\geq 37 weeks of gestation) in the fresh cycle, the cryopreserved cycles and cumulatively
- Time from start of controlled ovarian stimulation to live birth of a singleton born at term across the fresh and cryopreserved cycles, including duration and number of cycles before achieving a live birth of a singleton born at term

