8.3 Adverse Events of Special Interest

8.3.1 Ovarian Hyperstimulation Syndrome

Symptoms and Classification

OHSS is an adverse event of special interest during controlled ovarian stimulation. Investigators will record OHSS symptoms using a classification system based on Golan's classification system³¹ as shown in Table 8-1 to grade (1, 2, 3, 4 or 5) each OHSS case.

Table 8-1 Classification of Mild, Moderate and Severe OHSS (Based on Golan's Classification System)

Mild OHSS		
Grade 1	Abdominal distension and discomfort	
Grade 2	Features of grade 1 plus nausea/vomiting and/or diarrhea. Ovaries enlarged to 5-12 cm. ^{a)}	
Moderate OHSS		
Grade 3	Features of mild OHSS plus ultrasonic evidence of ascites. ^{b)}	
Severe OHSS		
Grade 4	Features of moderate OHSS plus clinical evidence of ascites and/or hydrothorax (or breathing difficulties). Paracentesis due to OHSS symptoms. ^{c)}	
Grade 5	All of the above plus change in blood volume, increased blood viscosity due to hemoconcentration, coagulation abnormalities, and diminished renal perfusion and function. d) Hospitalization due to OHSS symptoms. e)	

^{a)} For each ovary, the size will be the average of the greatest diameter and its greatest perpendicular diameter. Ovarian enlargement will be based on the average size of the right and left ovaries. The sizes of both ovaries should be recorded.

- c) In case of paracentesis, the volume of fluid drained should be measured.
- d) Hemoconcentration is defined as hematocrit >45 %. Electrolyte disturbances is defined as hyponatremia (sodium <135 mEq/L) and/or hyperkalemia (potassium >5.0 mEq/L). Coagulation abnormalities are defined as presence of thromboembolic events, abnormal prothrombin time or abnormal activated partial thrombin time. Diminished renal perfusion is defined as creatinine >1.2 mg/dl. Oliguria is defined as urine output less than 500 mL / 24 hours. Anuria is defined as failure to produce urine. If applicable, actual volume of urine output will be recorded.
- e) Hospitalization is defined as admission exceeding 24 hours.

b) For subjects with transvaginal evidence of ascites, the size of the fluid pockets in the pelvis (Douglas pouch, vesicouterine pouch, etc.) should be estimated by measuring the greatest diameter and its greatest perpendicular diameter, and multiplying these two numbers (the unit will be cm²). Peritoneal fluid is the total size of all fluid pockets in the pelvis.

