- Number of cryopreserved cycles initiated within 12 months from the start of controlled ovarian stimulation, and number and percentage of cryopreserved cycles with blastocyst transfer

- Circulating concentrations of AMH, FSH, LH, estradiol, progesterone, inhibin A and inhibin B on stimulation day 5, end-of-stimulation and oocyte retrieval, and FSH population pharmacokinetic parameters
- Total gonadotropin dose, number of stimulation days and number of dose adjustments
- Frequency and intensity of adverse events
- Changes in circulating levels of clinical chemistry and haematology parameters and proportion of subjects with markedly abnormal changes
- Frequency and intensity of injection site reactions (redness, pain, itching, swelling and bruising) assessed by the subject during the stimulation period
- Proportion of subjects with treatment-induced anti-FSH antibodies, overall as well as with neutralizing capacity
- Frequency and intensity of immune-related adverse events
- Proportion of subjects with cycle cancellations due to an adverse event, including immunerelated adverse events, or due to technical malfunctions of the administration pen
- Proportion of subjects with OHSS, overall and by grade, and proportion of subjects with moderate/severe OHSS
- Proportion of subjects hospitalized due to OHSS and proportion of subjects undergoing paracentesis due to OHSS
- Rate of multi-fetal gestation, biochemical pregnancy, spontaneous abortion, ectopic pregnancy (with and without medical/surgical intervention) and vanishing twins in the fresh cycle and in the cryopreserved cycles
- Technical malfunctions of the administration pen

Post-trial Endpoints

- Cumulative live birth rate after the fresh cycle and cryopreserved cycles initiated within 12 months from the start of controlled ovarian stimulation
- Live birth rate in the fresh cycle and in the cryopreserved cycles
- Live birth rate of singletons born at term (≥37 weeks of gestation) in the fresh cycle, the cryopreserved cycles and cumulatively
- Time from start of controlled ovarian stimulation to live birth of a singleton born at term across the fresh and cryopreserved cycles, including duration and number of cycles before achieving a live birth of a singleton born at term
- Rate of minor/major congenital anomalies at birth, 4 weeks and 1 year after birth in the fresh cycle and cryopreserved cycles

3 Trial Design and Sample Size Considerations

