10.3.3 Markedly Abnormal Changes

A summary table will be prepared displaying the proportion of subjects who have at least one markedly abnormal value. The table will also include a break-down by classification of the baseline value. Markedly abnormal criteria for the clinical chemistry and haematology variables are specified in Appendix 1.

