Appendix 1 Markedly Abnormal Laboratory Safety Values and Vital Signs

		Markedly abnormal criteria	
Variable	Unit	Low	High
Alanine transaminase (ALT)	IU/L	Not applicable	> 3xULN
Albumin	g/L	< 20	Not applicable
Alkaline phosphatase	IU/L	Not applicable	> 3xULN
Aspartate aminotransferase (AST)	IU/L	Not applicable	> 3xULN
Bicarbonate	mmol/L	< 15.1	> 34.9
Bilirubin direct	µmol/L	Not applicable	> 2xULN
Bilirubin total	µmol/L	Not applicable	> 2xULN
Blood urea nitrogen	mmol/L	Not applicable	> 12.5
Calcium	mmol/L	< 1.75	> 2.74
Chloride	mmol/L	Not applicable	Not applicable
Cholesterol total	mmol/L	Not applicable	> 10.34
Creatinine	µmol/L	Not applicable	> 3xULN
Gamma-glutamyl transpeptidase (GGT)	IU/L	Not applicable	> 3xULN
Glucose	mmol/L	< 2.5	> 16.7
Lactate dehydrogenase (LDH)	IU/L	Not applicable	> 3xULN
Phosphorus	mmol/L	< 0.6	Not applicable
Potassium	mmol/L	< 3.0	> 5.8
Sodium	mmol/L	< 125	> 155
Total protein	g/L	< 20	> 90
Uric acid	µmol/L	Not applicable	> 595

Table 4 Markedly Abnormal Criteria for Laboratory Tests – Clinical Chemistry

	Unit	Markedly abnormal criteria	
Variable		Low	High
Red blood cells	10 ¹² /L	< 3.0	Not applicable
White blood cells	10 ⁹ /L	< 2.5	> 15.0
Hemoglobin	g/L	< 100	> 190
Hematocrit	Ratio	< 0.28	> 0.50
Platelets	10 ⁹ /L	< 110	> 600
Red blood cell morphology			
MCV	fL	Not applicable	Not applicable
MCH	Pg	Not applicable	Not applicable
MCHC	g/L	Not applicable	Not applicable
White blood cell morphology			
Eosinophils	%	Not applicable	≥ 10
Neutrophils	%	≤ 15	≥ 90
Lymphocytes	%	≤ 10	≥ 80
Monocytes	%	Not applicable	≥ 20
Basophils	%	Not applicable	≥ 5
Bands	%	Not applicable	≥ 20

Table 5 Markedly Abnormal Criteria for Laboratory Tests – Hematology

Table 6	Markedly Abnormal Criteria for Vital Signs*	
---------	---	--

Variable	Criterion Value	Change from Baseline
Systolic blood pressure	≥ 180 mmHg	Increase of $\geq 20 \text{ mmHg}$
	\leq 90 mmHg	Decrease of ≥ 20 mmHg
Diastolic blood pressure	≥ 105 mmHg	Increase of $\geq 15 \text{ mmHg}$
	\leq 50 mmHg	Decrease of $\geq 15 \text{ mmHg}$
Pulse	≥ 120 bpm	Increase of ≥ 15 bpm
	\leq 50 bpm	Decrease of ≥ 15 bpm

* To be identified as markedly abnormal, a treatment value must meet the criterion value and also the specified change from baseline.

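### The laboratory endpoint is defined as markedly abnormal changes, but its table counts markedly abnormal values, with no post-dose or worsening condition

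*Protocol*

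**What the plan says.** Protocol 2.2 lists the secondary endpoint as "Changes in circulating levels of clinical chemistry and hematology parameters and proportion of subjects with markedly abnormal changes". SAP 2.2 repeats it, and SAP 10.3.3 carries a heading that speaks of changes.

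The analysis text in both documents is about values: "A summary table will be prepared displaying the proportion of subjects who have at least one markedly abnormal value". It continues: "The table will also include a break-down by classification of the baseline value". SAP 10.3.3 then states: "Markedly abnormal criteria for the clinical chemistry and haematology variables are specified in Appendix 1".

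In that appendix, Tables 4 (chemistry) and 5 (hematology) give low and high limits on the value only. Table 6 (vital signs) adds a change column, and its footnote reads: "To be identified as markedly abnormal, a treatment value must meet the criterion value and also the specified change from baseline".

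Protocol 7.2.2 and SAP 10.3 schedule the laboratory samples at screening, end-of-stimulation and end-of-cycle in the fresh cycle.

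**The concern.** An endpoint about change should respond to what happens after dosing. As written, the rule also responds to the state in which a woman entered the trial. A woman whose result lay past an Appendix 1 limit at screening and stayed there meets the rule. Read literally, so does a woman whose only qualifying result is the screening sample.

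The endpoint rate would then mix pre-existing abnormality with abnormality that arose on treatment. Randomization should spread the former evenly on average, but with about 50 placebo subjects one or two such women can shift the comparison visibly. The vital-sign rule in the same appendix shows that the SAP authors knew how to write the condition. It is missing for the laboratory data.

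**Working it through.** The plan gives no figure for this endpoint, so the check sets the texts side by side and runs simple cases through them.

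**Step 1: the two rules in Appendix 1.**

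| Condition | Laboratory (Tables 4, 5) | Vital signs (Table 6) |
|---|---|---|
| Limit on the value | yes | yes |
| Must be a treatment value | not stated | yes |
| Change from baseline required | no criterion has it | all six criteria have it |

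**Step 2: cases through the laboratory rule.** The low hemoglobin limit in Table 5 is below 100 g/L. The values in the cases are illustrations. I assume that the laboratory's lower reference limit is above 105 g/L, so that all three women are classed low at baseline.

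| Woman | Screening | After dosing | Counted as written | Counted under a new-or-worsened rule |
|---|---|---|---|---|
| A | 95 | 95 | yes | no, baseline line |
| B | 105 | 95 | yes | yes |
| C | 95 | 105 | yes, if read literally | no, baseline line |

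A did not change, B worsened and C improved. All three fall in the same low-baseline row, so a low/normal/high break-down cannot tell them apart. It does isolate a woman who starts normal and becomes markedly abnormal. Neither document says which classification is meant; low/normal/high is the one used for the shift tables. A break-down by whether baseline already met the Appendix 1 limit would separate A from B, but the text does not say that.

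**Step 3: can such women be enrolled?** Exclusion criterion 13 (protocol 4.1.2) removes a woman only when the investigator deems the abnormal screening result clinically significant. It does not refer to the Appendix 1 limits. Enrollment past a limit is therefore possible, though less likely.

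**Step 4: weight of one woman.** With the planned 500 and 50 subjects, each counted woman adds 1/500 = 0.2 percentage points to the FE 999049 rate or 1/50 = 2 percentage points to the placebo rate. The number of such women is not given and cannot be derived; zero is possible.

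**Step 5: a side check on Table 4.** Albumin and total protein share the low limit of below 20 g/L. Total protein = albumin + globulins, so total protein is at least as large as albumin, and total protein below 20 forces albumin below 20. Where both are measured, the low total-protein limit cannot add a woman to the count. The high limit (above 90 g/L) can.

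**The case against.** The best defense is that the table does not stand alone. Change from baseline is tabulated for every laboratory variable, shift tables compare baseline with the two later visits, and listings flag out-of-range and markedly abnormal values by subject and time point. An unchanged woman can be found there. The break-down by baseline class also suggests that the authors had post-baseline values in mind. Exclusion criterion 13 thins out the affected group, and the display is descriptive, with no test resting on it. All of this stands. It limits the consequence, but it does not make the endpoint's own table measure the endpoint.

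Three stronger readings are tempting, and the documents do not support them.

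- **A count of affected women.** A reader might assume a prevalence at screening and compare the result with the 0.5% incidence in protocol 9.1. No prevalence is given, and the 0.5% concerns the chance of seeing at least one rare event among 500 women. It is not a yardstick for this table.
- **Blindness to OHSS.** Footnote d to protocol Table 8-1 uses hematocrit above 45%, sodium below 135, potassium above 5.0 and creatinine above 1.2 mg/dL. Appendix 1 uses above 0.50, below 125, above 5.8 and above three times the upper limit of normal. A woman can meet the first set and none of the second. That is not an error. Nothing assigns OHSS laboratory signs to this table, the sodium and potassium limits appear only in the footnote and not in the grade 5 text, and laboratory values alone do not make grade 5. OHSS has its own tabulation by grade, its own work-up and narratives, and severe cases are reported as SAEs.
- **Inability to show protein loss.** Albumin below 20 g/L is still flagged, and both proteins appear in the shift and change tables. The redundant limit loses no case.

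**Conclusion.** The concern holds for the mismatch between endpoint and table. The endpoint names changes, while the rule counts values without a post-dose or worsening condition. This follows from the text alone. That the baseline break-down leaves the groups mixed rests on reading its classification as low/normal/high.

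The size is unknown and may be small. The documents support only the weight per affected woman: 0.2 percentage points in the FE 999049 group and 2 in the placebo group. No efficacy conclusion depends on it. It is worth correcting because the correction is cheap and this table is the planned report of a named secondary endpoint. The total-protein limit is a minor note.

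**What to change.** In SAP 10.3.3, and in protocol 9.8.2.2 so that the two agree, count a subject only if a value after first dose meets the Appendix 1 criterion and her baseline value either did not already meet it or has worsened further in the same direction. State what counts as further worsening. Show subjects already markedly abnormal at baseline on a separate line, and say which classification the baseline break-down uses. If the protocol text is left as it is, record the rule in SAP section 14, which at present declares no deviations from the planned analyses.

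The data exist: protocol 6.1.1 requires the screening chemistry and hematology results before randomization. The cost is wording, programming and a few more table rows, and the rule should be settled before unblinding.

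The sponsor should also check whether the low total-protein limit is intended. Any summary of laboratory results from OHSS work-ups should be kept apart from this table, because those samples are taken only in symptomatic women and would make ascertainment uneven.
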